Death, MI, and stroke will be evaluated at 3 years from the last patient randomized, where subjects contribute data from time of enrollment until the occurrence of MACCE or three year follow-up, whichever occurs first. Subjects who die or are lost to follow up before this time will be censored at their last recorded activity. This secondary endpoint is not a co-primary endpoint because we would need to adjust for multiplicity and this would increase our sample size.

Other Secondary Endpoints

- Comparison of proportion of patients in each arm with MACCE at one year, excluding patients lost to follow-up from each arm
- MACCE rate at each time point besides one year
- Rate of each individual component of MACCE at each time point
- Rate of death, MI, and stroke at each time point
- Rate of death and MI at each time point
- Rate of cardiac death alone and in combination with other end points
- Rate of death, MI, stroke and all repeat revascularizations at each time point
- Stent thrombosis (ARC definition) and graft occlusion at each time point
- Bleeding complication
- Significant arrhythmia
- Development of acute renal failure
- Length of hospital stay
- Rehospitalization within 30 days and 1 year of the primary procedure

- Usefulness of the STS, logistic Euroscore, SYNTAX score, clinical SYNTAX score, ACEF score, Functional SYNTAX score and other scoring systems for predicting outcomes
- Outcomes based on left internal mammary artery use alone versus multiple arterial conduits
- Cost and cost-effectiveness at each time point
- Health-related quality of life index (EQ-5D) at each time point
- Functional class at each time point
- Number of anti-anginal medications at each time point.

Pre-specified Subgroup Analyses

These analyses will be performed between the PCI and CABG arms, as well as within each arm, as appropriate.

- Comparison of outcomes by baseline features including diabetes status, sex, age, ejection fraction, kidney function, acute coronary syndrome, prior MI, and geographic location (within or outside of the United States).
- Comparison of outcomes by STS, logistic Euroscore, SYNTAX score, clinical SYNTAX score, ACEF score and Functional SYNTAX score
- Comparison of outcomes by revascularization status (i.e., complete or incomplete as defined by angiogram)
- Compare complete arterial revascularization to incomplete arterial revascularization in the CABG group
- Compare on-pump to off-pump CABG results

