- Comparison of outcomes by proximal LAD versus non proximal LAD
- Comparison of surgical results between patients with FFR measured before CABG and angiography-guided CABG

10. Statistics

Null and Alternative Hypotheses to Address Primary Question

The study makes use of a noninferiority design and assumes that a hazard ratio of 1.65 or less is not clinically meaningful. More specifically, the null hypothesis is that the hazard of MACCE for PCI patients is greater than that of CABG patients and the alternative hypothesis is that the hazard of MACCE for PCI is not worse (not greater) than that for CABG patients. Let HR_0 be the non-inferiority margin – i.e., the maximum ratio of clinical insignificance. Then the null (H0) and alternative (H1) hypotheses can be expressed as:

$$H_0: HR \geq HR_0 \text{ vs } H_1: HR < HR_0$$

Primary Analysis Plan: Statistical Tools and Test Statistic

The primary analysis will be based on the intention-to-treat (ITT) principle, whereby all randomized patients will be included in the analysis and according to the treatment group to which they were originally allocated. Patients will be encouraged to remain in the trial until completion of up to 5 years follow-up. All patients will be followed for 5 years post-randomization or until they die, whichever comes first. If a patient refuses further clinical follow-up, the follow-up evaluation will be conducted using telephone interviews. For patients who drop out or are lost to follow-up, the reason for dropping out or being lost will be recorded. Importantly, for the primary analysis the patient will be censored at the time when the last follow-up examination or telephone contact took place if the subject did not experience MACCE, allowing the subject to be included in the analysis according to the ITT analysis plan.

Kaplan-Meier curves will be used to graphically display differences in MACCE by treatment arm and by diabetes status. In addition, we will use survival analytic techniques such as a log-rank test or, if appropriate, a Cox proportional hazards (PH) model to estimate the difference in hazard of MACCE by treatment arm, stratified by center, and with diabetes status included as a term in the model. The test for non-inferiority of fractional flow reserve-guided PCI will be one-sided and assessed at the 0.025 level of significance. For example, a Cox PH model for the hazard of MACCE can be expressed as:

$$\lambda_1 = \lambda_{0i} \exp(\beta_1 PCI + \beta_2 DM)$$

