Our current approach is to do an intent-to-treat analysis and include all randomized subjects in the analysis. Subjects who are lost to follow-up will be included in the analysis up to the time they are censored. An alternative set of analyses that will serve as sensitivity analyses will be to compare the proportion of subjects who experience the primary event at one year of follow-up by treatment arm using logistic regression techniques, where subjects who are lost to follow-up are excluded from the analysis, or included with an imputed outcome using multiple imputation techniques that rely on missing at random and missing not at random techniques. Auxiliary variables to be used in the multiple imputation include all baseline variables such as age, gender, site, diabetes status, etc. This will allow comparisons to our primary analysis. If results are similar across analyses, this will bolster our findings. If they are different, we will report the discrepancy. The results from our primary analysis, however, will be reported as our final analysis.

Secondary Analyses

Secondary analyses will be performed to inform future studies and are therefore considered hypothesis-generating. For example, we will use Cox proportional hazards regression techniques to assess whether the differences in hazard of the key secondary outcome of death, MI, and stroke (censored at 3 years) is different by treatment arms. Similarly, we will use these tools to investigate whether relationships between outcome and treatment vary by baseline features such as age, sex, geographic location, etc.

11. Appendix A.

Definitions

Death is defined as all cause death. Cardiac death is defined as any sudden death, death related to acute myocardial infarction, arrhythmia or congestive heart failure, death secondary to a cerebrovascular accident, or death directly related to PCI or CABG, even if the ultimate cause of death is not clearly a cardiac event (e.g., infection). Non-cardiac death is any death which is not clearly cardiac in etiology.

Myocardial infarction is defined in two ways, depending on whether or not it is PCI or CABG-related or a spontaneous event, as recently described in the literature.²¹

Spontaneous myocardial infarction (>72 hours after PCI or CABG):

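### As written, the one-year proportion analyses do not use MACCE and event-free time recorded before a patient is lost, so they waste events or can bias the rate, depending on the reading

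*Combined protocol and SAP*

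**What the plan says.** Section 10, Sensitivity Analyses, sets out to "compare the proportion of subjects who experience the primary event at one year of follow-up by treatment arm using logistic regression techniques", with lost patients handled as follows: "where subjects who are lost to follow-up are excluded from the analysis, or included with an imputed outcome using multiple imputation techniques". The imputation methods are ones "that rely on missing at random and missing not at random techniques". On predictors the section says: "Auxiliary variables to be used in the multiple imputation include all baseline variables such as age, gender, site, diabetes status, etc".

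Section 9 puts the complete-case version first among the other secondary endpoints: "Comparison of proportion of patients in each arm with MACCE at one year, excluding patients lost to follow-up from each arm".

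The primary analysis treats the same patients differently. "Subjects who are lost to follow-up will be included in the analysis up to the time they are censored", and under Primary Analysis Plan a patient is censored at the last examination or "telephone contact took place if the subject did not experience MACCE". So a MACCE before loss counts there, and so does event-free time.

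Agreement between the analyses is to be taken as support and disagreement is to be reported, but "The results from our primary analysis, however, will be reported as our final analysis".

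For the proportion analyses the plan does not say how to classify a patient who has a MACCE and is later lost, whether imputation takes account of how long a patient was already event-free, or what the missing-not-at-random scenarios are.

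**The concern.** A sensitivity analysis for loss to follow-up should vary the assumption about the unseen data and keep the observed data fixed. Here the observed data change too. A patient with an infarction in week 1 who withdraws in month 4 has a known one-year outcome, yet the wording allows that patient to be dropped. A patient followed event-free for eleven months may be dropped, or may be given something close to a full-year risk.

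At stake is how any discrepancy is interpreted. If the logistic result differs from the primary one, or happens to agree, the cause may be the handling of partial follow-up rather than the missing data. One arm is open surgery, so different loss by arm is plausible. Two programmers could also build different datasets from the same text.

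**Working it through.** **The plan's own figure.** These analyses have none. The nearest is the sample size: events = 4(1.960 + 1.282)² / (ln 1.65)² = 167.6; at a mean one-year rate of 13% (10% and 16%), 167.6 / 0.13 / 2 = 645 per group, as stated. Nothing in this point enters that figure.

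**Inputs from the documents.** CABG one-year MACCE 10%, tolerated PCI rate 16%, margin HR 1.65 (Section 10, Sample Size). A year is 360 days (Section 6, Follow-up). No loss rate is given. The step from 1290 to at most 1500 patients implies a ceiling of 210/1500 = 14.0%.

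**Assumptions.** Loss L of 2%, 5% or 14%, uniform over the year and independent of outcome; 30% of one-year events in days 0-7 and the rest uniform.

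**Step 1: share q of a lost patient's events that come before loss.** q = 0.30 × (1 − 3.5/360) + 0.70 × 0.5 = 0.647. Of all lost patients, 0.10 × 0.647 = 6.47% have a recorded MACCE first.

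**Step 2: drop every lost patient.** Rate = 0.86 × 0.10 / 0.86 = 10.0%, so no bias. Observed events thrown away at 14% loss: 0.14 × 0.0647 / (0.86 × 0.10 + 0.14 × 0.0647) = 0.00906 / 0.09506 = 9.5%. If deaths cannot be followed by loss (15% of first events fatal, assumed), simulation gives 10.03-10.07% at 2-5% loss and at most 10.16% at 14%.

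**Step 3: keep MACCE before loss, drop event-free losses.** Rate = [(1 − L) × 0.10 + L × 0.0647] / [(1 − L) + L × 0.0647].
- L = 2%: 0.09929 / 0.98129 = 10.1%
- L = 5%: 0.09824 / 0.95324 = 10.3%
- L = 14%: 0.09506 / 0.86906 = 10.9%

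At 14% loss, with 0%, 30% or 50% of events in week 1, the result is 10.7%, 10.9% or 11.1%. A simulation with different timing (50% of CABG and 30% of PCI events in the first 30 days) gives 10.9-11.0%. For a true 16% it gives 17.3%.

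**Step 4: impute event-free losses from baseline only.** With uninformative covariates they receive the complete-case 10.9%, so the total stays at 10.9%. Their true residual risk is 0.10 × 0.353 / (1 − 0.0647) = 3.8%. For a patient event-free at day 300, residual risk is 1 − 0.9^(60/360) = 1.7% with a constant hazard, or 1.0% if half the events fall in the first 30 days. Baseline-only imputation assigns about 10%.

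**Step 5: comparison of arms, loss independent of outcome.**
- Equal 14% loss, true HR 1.66: the proportions imply 1.66 (all dropped) or 1.63 (events kept).
- Loss 14% CABG, 5% PCI, equal true risk, events kept: 10.9% vs 10.3%; odds ratio (0.1031/0.8969) / (0.1094/0.8906) = 0.94.
- Loss 10% vs 4%, events kept: a true HR of about 1.65 reads as 1.57 (more loss in CABG) or 1.70 (more loss in PCI); a true 1.0 reads as 0.95 or 1.04.

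**Step 6: loss that follows a MACCE, all lost patients dropped.** Assume loss in 5% of event-free patients and in 15% of those with a non-fatal event (85% of events).
- True 10%: 0.10 × (1 − 0.85 × 0.15) / [that + 0.90 × 0.95] = 0.08725 / 0.94225 = 9.3%.
- True 16%: 0.1396 / 0.9376 = 14.9%.
- If only PCI behaves this way and CABG loses 5% throughout (10.07%): HR = ln(1 − 0.1489) / ln(1 − 0.1007) = 1.52 against a true 1.65.

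**Step 7: use the recorded data.** Under independent loss, Kaplan-Meier returned the true 10.0% and 16.0% in every setting. In Step 6 it would count each MACCE before the loss, so that distortion would not arise.

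**The case against.** The strongest reply has five parts.

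1. A patient with a MACCE already has a known outcome. Sections 1 and 9 have patients contribute data until MACCE or one year, so such a patient may never be classed as lost. This stands as a reasonable reading: discarding events is the literal wording, not an explicit rule. But the primary analysis adds the qualifier about no prior MACCE, and the proportion analyses omit it.

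2. A reader might infer that the plan both discards events and yields wrong MACCE rates. The documents do not support the two together. If every lost patient goes and loss is non-informative, the rate is nearly right (Step 2). The upward bias appears when events are kept and only event-free losses leave.

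3. A reader might also infer that imputation is restricted to baseline variables. The list is introduced as inclusive and left open-ended, so time of loss is unmentioned, not ruled out.

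4. Missing-not-at-random imputation is planned, and it addresses informative censoring that the primary model assumes away. Calling the whole set a poor check would go too far. What remains is that no scenario is specified and no use of time already survived is stated.

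5. The effect is small. At 2-5% loss the bias is 0.1-0.3 points. Even 14% vs 5% loss gives about 0.6 points, against a standard error of √(2 × 0.10 × 0.90 / 750) = 1.5 points. Kaplan-Meier curves by arm are already planned. All of this is correct, and it limits the point to the supportive analyses.

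**Conclusion.** The point holds in limited form. As written, the one-year proportion analyses do not use MACCE and event-free time that the primary analysis uses. At 14% loss the cost is either about 10% of observed events wasted with a nearly unbiased rate, or a true 10% reading as about 10.9%. At 2-5% loss the second reading gives 10.1-10.3%. The comparison of arms hardly moves under equal, non-informative loss. It moves materially when loss is unequal or informative: a true HR of about 1.65 can read as 1.52 to 1.70 in the settings examined.

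All sizes rest on assumed loss rates, loss patterns and event timing, because the plan states none of them; 14% is only the ceiling implied by the enrolment allowance. It would be wrong to conclude that the non-inferiority result is compromised: the primary analysis, its status as the final result and the sample size are untouched.

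**What to change.** - In Section 9 (Other Secondary Endpoints) and Section 10 (Sensitivity Analyses), state that a MACCE before loss always counts as an event, and that lost means event-free at last contact before one year.
- Report Kaplan-Meier one-year risks by arm and their difference with a confidence interval, in place of or beside the complete-case proportion.
- In the planned imputation under both missingness assumptions, impute only event-free losses, conditional on arm, baseline covariates and being event-free to the loss date.
- Specify the missing-not-at-random version as a range of multipliers on the post-loss hazard, varied by arm, for example raising it in the PCI arm until non-inferiority is lost.

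The cost is a few sentences in the plan and modest extra programming. The event and last-contact dates are already needed for the primary analysis, which does not change.

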Intraocular bleed compromising vision

Type 4: CABG-related bleeding

Perioperative intracranial bleeding within 48 h

Reoperation after closure of sternotomy for the purpose of controlling bleeding

Transfusion of ≥ 5 U whole blood or packed red blood cells within a 48-h period†

Chest tube output ≥ 2 L within a 24-h period

Type 5: fatal bleeding

Type 5a

Probable fatal bleeding; no autopsy or imaging confirmation but clinically suspicious

Type 5b

Definite fatal bleeding; overt bleeding or autopsy or imaging confirmation

Stent thrombosis is defined as per the Academic Research Consortium.²³

ARC Definitions:

Definite stent thrombosis

1. Angiographic confirmation of stent thrombosis
2. The presence of a thrombus that originates in the stent or in the segment 5 mm proximal or distal to the stent and presence of at least 1 of the following criteria within a 48-hour time window:
 - Acute onset of ischemic symptoms at rest
 - New ischemic ECG changes that suggest acute ischemia
 - Typical rise and fall in cardiac biomarkers (refer to definition of spontaneous MI)
 - Nonocclusive thrombus
 - Intracoronary thrombus is defined as a (spheric, ovoid, or irregular) noncalcified filling defect or lucency surrounded by contrast material (on 3 sides or within a coronary

stenosis) seen in multiple projections, or persistence of contrast material within the lumen, or a visible embolization of intraluminal material downstream.

- Occlusive thrombus
- TIMI 0 or TIMI 1 intrastent or proximal to a stent up to the most adjacent proximal side branch or main branch (if originates from the side branch).
- Pathological confirmation of stent thrombosis
- Evidence of recent thrombus within the stent determined at autopsy or via examination of tissue retrieved following thrombectomy.

Probable stent thrombosis

Clinical definition of probable stent thrombosis is considered to have occurred after intracoronary stenting in the following cases:

- Any unexplained death within the first 30 days
- Irrespective of the time after the index procedure, any MI that is related to documented acute ischemia in the territory of the implanted stent without angiographic confirmation of stent thrombosis and in the absence of any other obvious cause

Possible stent thrombosis

Clinical definition of possible stent thrombosis is considered to have occurred with any unexplained death from 30 days after intracoronary stenting until end of trial follow-up.

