Graft Occlusion is defined based on an ARC-like definition²⁴

Definite graft occlusion

1. Clinical presentation of acute coronary syndrome with graft occlusion confirmed by angiography, multi-slice CT or autopsy
2. Q-wave MI in the territory of one or more of the treated vessels within the first 30 days

Probably graft occlusion

1. Any unexplained death within 30 days of CABG
2. Any MI that is related to documented acute ischemia in the territory of the anastomosed graft without angiographic confirmation of graft occlusion

Possible graft occlusion

1. Any unexplained death beyond 30 days

Significant Arrhythmia consists of ventricular tachycardia or fibrillation requiring cardioversion, atrial fibrillation lasting > 24 hours, or need for a permanent pacemaker.

Acute Kidney Injury AKI (acute kidney injury) is defined as any of the following:

- K Increase in SCr (Serum creatinine) by ≥ 0.3 mg/dl (≥ 26.5 $\mu\text{mol/l}$) within 48 hours;
- or K Increase in SCr to ≥ 1.5 times baseline, which is known or presumed to have occurred within the prior 7 days;
- or K Urine volume < 0.5 ml/kg/h for 6 hours.

Rehospitalization is defined as a hospital stay of > 36 hours.

Cross-over

If, during the first month after randomization, a patient receives as the initial revascularization therapy the alternative form of revascularization than the assigned treatment (i.e. Randomized to CABG but receives PCI), this will be defined as a cross-over and not a repeat revascularization event, unless the reason for the alternative revascularization strategy is due to a change in the patient's clinical status resulting in urgent/emergent revascularization.

12. References

¹ Fihn SD, Gardin JM, Abrams J, Berra K, Blankenship JC, Dallas AP, Douglas PS, Foody JM, Gerber TC, Hinderliter AL, King SB 3rd, Kligfield PD, Krumholz HM, Kwong RY, Lim MJ, Linderbaum JA, Mack MJ, Munger MA, Prager RL, Sabik JF, Shaw LJ, Sikkema JD, Smith CR Jr, Smith SC Jr, Spertus JA, Williams SV, Anderson JL. 2012 ACCF/AHA/ACP/AATS/PCNA/SCAI/STS guideline for the diagnosis and management of patients with stable ischemic heart disease: a report of the American College of Cardiology Foundation/American Heart Association task force on practice guidelines, and the American College of Physicians, American Association for Thoracic Surgery, Preventive Cardiovascular Nurses Association, Society for Cardiovascular Angiography and Interventions, and Society of Thoracic Surgeons. *Circulation* 2012;126:e354-471.

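### An unexplained death that is neither sudden nor procedure-related defaults to non-cardiac, yet the same appendix counts it as probable or possible stent thrombosis or graft occlusion

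*Combined protocol and SAP*

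**What the plan says.** Section 11 (Appendix A, Definitions) takes death as all-cause and then divides it. The cardiac list begins "Cardiac death is defined as any sudden death, death related to acute myocardial infarction, arrhythmia or congestive heart failure". It continues with death from a cerebrovascular accident and with procedural deaths, including those whose final cause is something like infection. Everything else falls under one sentence: "Non-cardiac death is any death which is not clearly cardiac in etiology". Neither part names unexplained death or death of unknown cause.

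Later in the same appendix, unexplained death is a criterion in its own right:

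- Probable stent thrombosis: "Any unexplained death within the first 30 days".
- Possible stent thrombosis: "any unexplained death from 30 days after intracoronary stenting until end of trial follow-up".
- Probable graft occlusion: "Any unexplained death within 30 days of CABG".
- Possible graft occlusion: "Any unexplained death beyond 30 days".

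None of these four criteria makes an exception for a death ruled non-cardiac.

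Section 9 (Other Secondary Endpoints) reports both outcomes. One item is "Rate of cardiac death alone and in combination with other end points". Another is stent thrombosis and graft occlusion at each time point, without saying whether only definite events count or probable and possible ones too.

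**The concern.** The two parts of the appendix use opposite defaults for the same missing information. Where the cause of a death cannot be established, the death definition presumes it was not cardiac, while the stent and graft definitions presume, with graded certainty, that it was coronary. A patient can then appear as a non-cardiac death in one secondary table and as a probable stent thrombosis or graft occlusion in another.

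Such deaths are foreseeable. Under Section 6 (Follow-up), contact at 6 months and 2 years is by telephone and nothing is scheduled between years 3 and 5. Section 10 provides telephone interviews for patients who refuse clinical follow-up. Some late deaths may come with little information on cause.

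What is at stake is the readability of the cardiac-death endpoint. Section 3 shows why it will be looked at: it quotes cardiac death in SYNTAX as 3.7% with PCI against 2.1% with CABG at one year, and 6.0% against 3.6% at three years.

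**Working it through.** The plan gives no figure on this point, so the check is mainly a reading of the definitions against each other. The table takes each kind of death in a patient who has received a stent or a graft.

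| Kind of death | Death definition | Stent/graft definition | Consistent? |
|---|---|---|---|
| Sudden, cause not found | Cardiac | Probable (within 30 days) or possible (later) | Yes |
| Directly related to PCI or CABG, e.g. infection | Cardiac | Explained, so this criterion is not met | Yes |
| Non-cardiac cause established | Non-cardiac | Explained, so this criterion is not met | Yes |
| Unexplained, not shown to be sudden, not procedure-related, within 30 days | Non-cardiac, by the residual sentence | Probable | No |
| The same, later | Non-cardiac, by the residual sentence | Possible | In tension, but not strictly opposed |

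The conflict is therefore confined to the last two rows and is sharpest in the fourth. *Possible* can coexist with an undetermined cause; *probable* sits badly beside *non-cardiac*. The boundary of the first row is itself loose, because the appendix does not define *sudden*. A patient found dead at home without a witness could fall on either side.

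There is also a small internal tension in the death definition. It counts as cardiac a "death directly related to PCI or CABG, even if the ultimate cause of death is not clearly a cardiac event (e.g., infection"), while the residual sentence sends any death not clearly cardiac the other way. Reading the specific clause as overriding the general one resolves this, but the text does not say so.

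**What a shift would look like.** Let u be the number of deaths in an arm that the residual sentence moves out of cardiac death. Assume 750 patients per arm (the enrolment ceiling of 1500, allocated 1:1).

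- One death moves the arm's rate by 1/750 = 0.13 percentage points.
- The difference between arms changes by (u for PCI − u for CABG)/750. If u is equal in the two arms, the absolute difference does not move.

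The documents give no value for u. For illustration only, apply the SYNTAX cardiac-death rates from Section 3, suppose they include unexplained deaths, and assume that the same share of cardiac deaths in each arm, 5% to 30%, would be moved:

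- One year: 750 × 0.037 = 27.75 and 750 × 0.021 = 15.75, a gap of 12.0 deaths. After the shift the gap is 12.0 × 0.95 = 11.4 down to 12.0 × 0.70 = 8.4.
- Three years: 750 × 0.060 = 45 and 750 × 0.036 = 27, a gap of 18 deaths. After the shift the gap is 18 × 0.95 = 17.1 down to 18 × 0.70 = 12.6.

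In this scenario the ratio between arms is unchanged; what is lost is absolute difference and precision. The SYNTAX figures include left main disease, which this trial excludes, so they show only how the arithmetic behaves.

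**The case against.** The strongest reply is that the gap is narrow and the plan has safeguards. Sudden deaths and procedure-related deaths are already cardiac, so a reader who inferred that all unexplained deaths are non-cardiac would be wrong. Unexplained deaths are never graded as definite stent thrombosis or graft occlusion. Section 8 has a blinded Clinical Events Committee rule on every death under explicit criteria. All-cause death is reported as a component of MACCE, so no death disappears. Preferring a specific definition of cardiac death to a sensitive one is a legitimate choice, and Section 10 calls the secondary analyses hypothesis-generating.

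Most of this stands, and it limits the point. It does not remove it. Section 8 ties the committee's criteria to the protocol. The committee may define *sudden* or *clearly*, but it cannot simply reverse a written default, and it starts from definitions that disagree. The choice of a specific definition is also not carried through, since the stent and graft definitions go the other way.

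A reader might further infer that the rule favours PCI, because peri-operative surgical deaths are captured as cardiac while late unexplained deaths after stenting are not. The text does not support this. The procedural clause names both PCI and CABG, the unexplained-death criteria cover both stents and grafts, and a death from peri-operative infection has a known cause, so it is not the counterpart of an unexplained one.

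**Conclusion.** The inconsistency is in the current text and nothing in the documents reconciles it. It affects unexplained deaths that are neither sudden nor procedure-related, and it matters most at the probable grade. Its practical reach also depends on whether probable and possible events are reported, which Section 9 leaves open.

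It is tempting to say that cardiac death *is* undercounted, or that the misclassified deaths rival the SYNTAX effect. Neither follows. The documents set no rule that unexplained deaths are cardiac, so the most that can be said is that cardiac death risks being undercounted relative to the stent and graft definitions. A number of deaths moved within each arm cannot be set against a difference between arms; only an imbalance, or an equal share of unequal totals, changes that difference. The size and the direction are both unknown.

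The primary and key secondary endpoints, the margin of 1.65 and the sample size of 645 per group do not depend on the split. This is a cheap improvement to endpoints listed as other secondary, worth making because the fault is a stated rule and not merely missing detail.

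**What to change.** Three changes:

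1. In Appendix A, replace the residual sentence with one to this effect: *a death is cardiac unless a non-cardiac cause is established; deaths of unknown or unexplained cause are cardiac.* Keep the rest of the definition. This also removes the tension with the procedural clause.
2. In Section 9, state which grades of stent thrombosis and graft occlusion (definite, probable, possible) the endpoint reports.
3. Tabulate unexplained deaths by arm, so that readers can see how much the default decides and can recount under the other rule.

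The cost is a sentence in the appendix, matching wording in the adjudication rules, a line in the endpoint list and one table. The downside is that a few truly non-cardiac deaths of unknown cause will be counted as cardiac in both arms; the table of unexplained deaths makes that visible.
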